### 3.4.2 Safety Objective and Endpoints

The safety objective of the study is to confirm survivorship of the Global Icon stemless shoulder at 24, 60 and 120 months postoperative and collect information related to the type and frequency of adverse events

The safety endpoints are:

- Overall survivorship of the GLOBAL ICON stemless humeral component survivorship at 24, 60 and 120 months post-operative, where the device is deemed to be surviving if no components (anchor plate and humeral head) have been removed for any reason
- The type and frequency of all adverse events (AEs) in this study will be summarised, with distinction of serious AEs, operative and device related AEs.

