**Table 2: Interval Windows**

Analysis Visit	Study Visit	Study Interval (Days from Surgery)	Visit Window
Baseline	Pre-Op	--180 days to day of surgery (day 0)	-180 to 0 days
Surgery	Surgery	0	
Immediate Post-Op	Immediate Post-Op	0-10	5 (-5 to +5 days)
3 Months	3 Months	35 – 126	80 ± 45 days
12 Months	12 Months	281 - 449	365 ± 84 days
24 Months	24 Months	646 - 1644	730 - 84 days 730 + 914 days
60 Months	60 Months	1645 - 2005	1825 ± 180 days

120 Months	120 Months	3470 – 3830	3650 ± 180 days
------------	------------	-------------	-----------------

The intervals defined in the visit window column will be used to determine if data are collected within the protocol specified visit windows. Data collected at planned and unscheduled visits will be allocated according to the visit windows based on the collection date. The primary endpoint will use the data collected within the 24-month interval window. Secondary and tertiary endpoints will make use of the analysis visit, that is, the visit to which the data are mapped. If multiple records are allocated to the same analysis visit and one of the records is the planned collection, that record will be maintained for the primary, secondary and tertiary analyses. If none of the records are from planned collections, the record closest to the target study day for the visit will be used. Any planned visits conducted outside of the window will be considered a protocol deviation.

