### 7.9.2 Safety Endpoints

1. Overall survivorship of the GLOBAL ICON device at 24, 60 and 120 months post-operative, where a subject is deemed to be surviving if no humeral components (anchor plate, humeral head) have been removed for any reason

An estimate of device survivorship of the GLOBAL ICON stemless humeral component will be presented using the Kaplan-Meier method. Removal of any humeral components, defined as revision, for any reason is the event of interest. Cases not revised will be censored at their date of last follow-up, death, or withdrawal from the study. Survivorship point estimates and 95% confidence intervals will be presented for a time point if at least 40 subjects remain at risk. The conventional Greenwood estimate will be used to calculate the variance and the complementary log-log transformation will be used to construct 95% confidence intervals using PROC LIFETEST.

2. The type and frequency of all adverse events (AEs) in this study will be summarised, with distinction of serious AEs, operative and device related AEs.

The type and frequency of AEs through 120 months post-operative will be presented in table form and via a listing. An overall summary of adverse events (AE) will be provided, including the number and the percent of subjects with all AEs, all serious AEs, all related AEs (device and procedure related), and all AEs by severity. In addition, all adverse events, serious, and non-serious adverse events will be summarised and tabulated by preferred term, both overall and by severity, and by time period of onset. As described in Section 7.4 Interval Windows will be implemented for the radiographic loosening endpoint.

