#### **7.9.4 Tertiary Endpoints**

All Tertiary endpoint analyses will be presented for the Safety Population as described in Table 3.

Tertiary endpoints in the study will include the following:

1. Mean change from baseline for the Constant-Murley Score at 3, 12, 24, 60 and 120 months post-operative
2. Mean change from baseline for the Oxford Shoulder Score at 3, 12, 24, 60 and 120 months post-operative
3. Mean change from baseline for EQ-5D-5L dimension score and EQ-VAS scores at 3, 12, 24, 60 and 120 months post-operative
4. Periprosthetic fracture survivorship of the GLOBAL ICON stemless humeral component at 24, 60 and 120 months post-operative.

The tertiary endpoints 1 through 3, above, will be analysed at each time point of interest in the same manner as described for the corresponding secondary endpoint with the modification post-surgical measurements will be represented as a change from baseline (with baseline measurement included as a covariate in a linear regression model). As described in Section 7.4 Interval Windows will be implemented for these endpoints (1 through 4).

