1.2 Safety Objective

The safety objective is to evaluate the overall survivorship of the device as well as to characterize adverse events. For overall survivorship, a device is deemed to be surviving if no components have been removed for any reason. Survival is based on Kaplan-Meier methodology, with survival reported at the last day of the 24-, 60- and 120-months post-operative assessment window (see section 4). For adverse events (AE), the type and

frequency of all AEs in this study will be summarized, with distinction of serious AEs, operative and device related AEs.

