1.4 Tertiary Objectives

Tertiary objectives are to evaluate levels of improvement, evaluated as a change from baseline for each post-operative assessment time point, for the adjusted Constant-Murley Score, Oxford Shoulder Score and EQ-5D-5L. This will be evaluated by examining change from baseline at 3-, 12-, 24-, 60-, and 120- month visits. Lastly, survival of the GLOBAL ICON stemless humeral component for the reason of periprosthetic fracture will be reported using Kaplan-Meier methodology. Survival will be reported on the last day of the 24-, 60- and 120-month assessment windows.

2. Treatment Assignment

Treatment assignment is described in Section 1.

3. Randomization and Blinding

Neither randomization nor blinding will be implemented in this study.

4. Interval Windows

Data collected throughout the study will be assessed for compliance with the protocol-specified visit schedule.

Table Seven windows are defined based on the number of days prior to or after surgery (Day 0): baseline, Immediate post-op, 3-months post-op, 12-months post-op, 24-months post-op, 60-months post-op and 120-months post-op. If multiple visits fall into the same interval, the result latest in the visit window with complete data will be used in the analysis.

Table 1. Interval Windows

Analysis Visit	Study Visit	Study Interval (Days from Surgery)	Visit Window
Baseline	Pre-Op	-180 days to day of surgery (day 0)	-180 to 0 days
Surgery	Surgery	0	
Immediate Post-Op	Immediate Post-Op	0-10	5 (-5 to +5 days)
3 Months	3 Months	35 – 126	80 ± 45 days
12 Months	12 Months	281 – 449	365 ± 84 days
24 Months	24 Months	646 - 1644	730 - 84 days 730 + 914 days
60 Months	60 Months	1645 - 2005	1825 ± 180 days
120 Months	120 Months	3470 – 3830	3650 ± 180 days

5. Description of Scales and Scoring

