9.6 Reporting of the Safety Endpoints

Survivorship of the GLOBAL ICON device at 24-, 60- and 120- months post-operative will be reported, where the device is deemed to be surviving if no humeral components (anchor plate, humeral head) have been removed for any reason. An estimate of device survivorship of the GLOBAL ICON implant will be presented using Kaplan-Meier methods. Removal of any component, defined as revision for any reason, is the event of interest. Cases not revised will be censored at their date of last follow-up, death (if a death occurred) or study end date. Survivorship point estimates and 95% confidence intervals will be presented for a time point if at least 40 subjects remain at risk. The conventional Greenwood estimate will be used to calculate the variance and the complementary log-log transformation will be used to construct 95% confidence intervals using PROC LIFETEST.

The type and frequency of all adverse events (AEs) in this study will be summarized, with distinction of serious AEs, operative and device related AEs. The type and frequency of AEs through 120 months post-operative will be presented in table form and via a listing. An overall summary of AEs will be provided, including the number and the percent of subjects with all AEs, all serious AEs, all related AEs (device and procedure related), and all AEs by severity. In addition, all adverse events, serious, and non-serious adverse events will be summarized and tabulated by preferred term, both overall and by severity, and by time period of onset.

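### SAP 1.2 and 1.4 read Kaplan-Meier survivorship on the last window day, so the 24-month figure is read at 54 months; whether a 120-month figure appears depends on an unsettled censoring date

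*SAP*

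**What the plan says.** **Reading day.** SAP 1.2 plans overall device survivorship by Kaplan-Meier, "with survival reported at the last day of the 24-, 60- and 120-months post-operative assessment window", and points to SAP Section 4 for the windows. SAP 1.4 has the same rule for periprosthetic fracture: "Survival will be reported on the last day of the 24-, 60- and 120-month assessment windows". SAP 1.3 applies it to aseptic loosening at every window.

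**Windows.** SAP Table 1 and Protocol Table 2 agree: 24 months is days 646 to 1644, 60 months is days 1645 to 2005, and 120 months is days 3470 to 3830.

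**Time points named elsewhere.** Protocol 3.4.2 defines the safety endpoint as "survivorship at 24, 60 and 120 months post-operative, where the device is deemed to be surviving" when no humeral component has been removed, and Protocol 7.9.2 names the same times. SAP 9.6 states: "Survivorship of the GLOBAL ICON device at 24-, 60- and 120- months post-operative will be reported". None of these three mentions the end of a window. Protocol 7.9.4 also names 24, 60 and 120 months for fracture survivorship, but adds "As described in Section 7.4 Interval Windows will be implemented for these endpoints (1 through 4"); it gives no reading day.

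**Censoring.** Protocol 7.9.2: "Cases not revised will be censored at their date of last follow-up, death, or withdrawal from the study". SAP 9.6: "Cases not revised will be censored at their date of last follow-up, death (if a death occurred) or study end date". SAP 9.8.2 censors withdrawals at the date of last assessment. Protocol 7.9.2 and SAP 9.6 and 9.7 show an estimate only where at least 40 subjects remain at risk.

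**The concern.** A programmer who follows SAP 9.6 and one who follows SAP 1.2 would report different numbers under the same 24-month label. The 24-month window is very asymmetric (84 days before target, 914 after), so its last day is 30 months past the label and one day before the 60-month window opens. A reader of the report would take the figure as two-year survivorship when it includes every removal up to four and a half years.

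The 120-month reading has a different problem. Day 3830 closes the last scheduled window. Depending on how unrevised cases are censored, the ten-year estimate is either withheld by the plan's own 40-at-risk rule or rests on time in which no visit is scheduled.

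**Working it through.** **1. Reproduce the window ends.** Target day plus upper allowance, divided by 30.4375 days per month:

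| Label | Last day | Months |
|---|---|---|
| 24 months | 730 + 914 = 1644 | 54.0 |
| 60 months | 1825 + 180 = 2005 | 65.9 |
| 120 months | 3650 + 180 = 3830 | 125.8 |

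All three days match the tables in both documents. Day 1644 is 1644/730 = 2.25 times the target day. The first two readings are 2005 - 1644 = 361 days apart, against 1825 - 730 = 1095 days between targets.

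**2. Size of the 24-month shift.** The documents give no removal rate, so a constant annual rate h is assumed, with S(t) = exp(-h × t/365.25):

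| h per year | S(730) | S(1644) | Difference (points) |
|---|---|---|---|
| 0.5% | 99.0% | 97.8% | 1.2 |
| 1% | 98.0% | 95.6% | 2.4 |
| 2% | 96.1% | 91.4% | 4.7 |

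At the same rates the shift from day 1825 to day 2005 is 0.2 to 0.9 points, and from day 3650 to day 3830 it is 0.2 to 0.8 points. Only the 24-month shift is notable. The direction needs no assumption, because a Kaplan-Meier curve never rises.

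**3. At risk on day 3830, censoring at last follow-up (Protocol 7.9.2).** Only subjects last seen on or after day 3830 count. Ten-year attendance is not given; 63 to 157 attendees (40 to 100% of 157) are assumed.

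- Visits uniform over the 361-day window: 157/361 = 0.43 expected with all 157 attending, 133/361 = 0.37 with 133.
- Visits normal about day 3650 and kept in window: fewer still. Across these in-window patterns, 20,000 simulations gave at most 6 at risk.
- Late visits allowed (normal, SD 90 days): mean 1.5 (63 attendees) to 3.6 (157), maximum 12.

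Reaching 40 would need 40/157 = 25% of subjects to be last seen on or after the closing day, even with full retention.

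**4. At risk on day 3830, completers carried to a study end date (SAP 9.6).** The date is undefined. Assume month 144 (24 months of enrolment plus 120 of follow-up, Protocol 4.1) and uniform enrolment. A subject reaches day 3830 before study end if enrolled in the first 144 - 125.83 = 18.17 months, and 18.17/24 = 76%. With 133 retained that is about 101 subjects, so the rule is met. None of them has a scheduled visit after the 120-month one.

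**5. Reading at day 3650 instead.** If visits are symmetric about the target, the number at risk is roughly Binomial(n, 0.5). The chance of at least 40 is 2% for n = 63, 54% for n = 80, 91% for n = 92 (59% of 157) and about 100% for n = 133.

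**6. Trade-off of reading at day 730.** Removals between days 730 and 1644 would number 157 × (S(730) - S(1644)) = 1.9, 3.8 or 7.4 at the three assumed rates. This is the ceiling on subjects who fail the composite yet count as surviving at day 730, reached only if every 24-month visit fell at the end of its window.

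**The case against.** The best defence is that naming 24 months is not naming day 730. Both documents define the 24-month visit as days 646 to 1644, SAP 1.2 fixes the day and cross-refers to the windows, and SAP 9.6 can be read as the label for that rule. Window-end reading also lines up with the primary composite, which includes component removal: Protocol 7.4 says "The primary endpoint will use the data collected within the 24-month interval window", and SAP Section 1 bases effectiveness and safety on data up to and including the 24-month visit. The consequences are limited too: SAP Section 6 tests no safety hypothesis and allows no labelling claim from safety endpoints, and the curve can be read on any day without new data.

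Much of this stands. The alignment with the composite is a real merit, though neither document gives it as the reason. For fracture survivorship the conflict is softer, because Protocol 7.9.4 applies the windows to that endpoint; Protocol 7.9.2 makes no such link for device survivorship. What does not stand is that a label can cover a 30-month gap.

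A reader might infer that the 120-month estimate is bound to be withheld. The documents do not support that: it follows from the Protocol's censoring rule, but step 4 shows that SAP 9.6 can be read so that the 40-at-risk rule is met. A reader might also infer that the Kaplan-Meier analysis planned for the US application (Protocol 7.10) will lack 40 subjects at day 1644. Its timing is not given, so this cannot be established.

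**Conclusion.** The concern holds for the reading day. SAP 1.2 and 1.4 are inconsistent with SAP 9.6 and, for device survivorship, with Protocol 3.4.2 and 7.9.2. Followed as written, they give a 24-month figure that describes 54 months. The size of the understatement rests on the assumed constant removal rates; the 54 months and the direction do not.

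At 120 months the finding is conditional: no estimate under censoring at last follow-up, or an estimate resting on unobserved time under one reading of SAP 9.6. Both are unsatisfactory, and the documents do not settle which applies.

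Nothing here favours the device or weakens the primary test. This is a descriptive safety read-out that should be corrected before it is reported.

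**What to change.** (a) In SAP 1.2, 1.4, 9.6 and 9.7, read device and fracture survivorship at days 730, 1825 and 3650, and reconcile the window sentence in Protocol 7.9.4.

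(b) Use one censoring rule in both documents: death, or the last date on which implant status was known. For withdrawals that is the last assessment, which reconciles Protocol 7.9.2 with SAP 9.8.2. Delete the study end date from SAP 9.6.

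(c) Keep the 40-at-risk rule as it is.

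(d) For radiographic loosening (SAP 1.3), a window-end reading may stay at the earlier visits if labelled with its actual day (for example day 1644, 54 months). Read the 120-month estimate at day 3650, because day 3830 has the same at-risk problem.

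The cost is SAP wording, the Protocol sentences on windows and censoring, and new reading days in PROC LIFETEST. No new data are needed, since the curve requires each removal date whichever day is read.

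There are two downsides. A removal between day 730 and a later in-window 24-month visit would fail the composite yet count as surviving at day 730. And the day-3650 estimate may still miss the 40-at-risk rule with heavy attrition (below about 92 attendees) or mostly early visits: if only 30% of 133 attendees are seen after day 3650, about 40 are at risk.

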1.3 Secondary Objectives

Secondary objectives include the assessment of clinical and radiographic performance post-operatively at 3-, 12-, 24-, 60- and 120-month visits. Assessments include: adjusted Constant-Murley Score, Oxford Shoulder Score, EQ-5D-5L and radiographic evidence of aseptic loosening of the GLOBAL ICON stemless humeral component. Of interest for the non-radiographic endpoints are mean values at the distinct time points. Based on radiographic data, time to aseptic loosening will be characterized by survival analysis using Kaplan-Meier methodology, where the event of interest is aseptic loosening. Survival will be reported at the last day of each assessment window.

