### 5.3.2 Radiographic Assessments

Radiographs will be taken at the following time points:

- Immediate post-operative (0-10 days) – only Grashey AP view required
- 3, 12, 24, 60 and 120 months post treatment – Grashey AP and Axillary view required

The investigator will not be required to complete any eCRF's for per protocol radiographic assessments.

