## 5.6 Subject Discontinuation

Subjects are free to withdraw their consent to participate in the study at any time.

Subjects may be withdrawn by the investigator if they consider that the subject is unable to fulfil their requirements of participation.

Subjects may be documented as lost to follow up at the end of the study where they have not formally withdrawn their consent, but do not attend all required follow up visits/study schedule assessments on the request of the investigator.

A subject will be documented as withdrawn in the event of their death during the study.

The maximum recruitment limit at each site applies to subjects that successfully receive the study device.

In the instance of a consented subject withdrawing from the study pre-operatively or intra-operatively, they can be replaced by the investigator with another suitable subject.

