### 7.9.3 Secondary Endpoints

All secondary endpoint analyses will be presented for the Safety Population as described in Table 3 above. For the purpose of analysis, baseline is defined as last available result prior to surgery.

Secondary endpoints in the study include the following:

1. Mean adjusted Constant-Murley Score at baseline and 3, 12, 24, 60 and 120 months post-operative
2. Mean Oxford Shoulder Score at baseline and 3, 12, 24, 60 and 120 months post-operative
3. Mean EQ-5D-5L Scores by dimension and EQ VAS, at baseline and 3, 12, 24, 60, and 120 months post-operative
4. Radiographic evidence of aseptic loosening of the GLOBAL ICON stemless humeral component immediate post-operative and 3, 12, 24, 60, and 120 months post-operative.

The number and percentage of radiographic evidence of loosening will be presented at each planned time point through 120 months, including estimates of survival.

Secondary endpoints 1 through 3, listed above, will be analysed identically, using descriptive summaries for continuous data, at baseline, and each follow up visit through 120 months. Where appropriate, analyses will also be presented for subscales, dimensions, components, or index values. For secondary endpoint the frequency and percent will be reported for each post-operative time. As described in Section 7.4 Interval Windows will be implemented for the above secondary endpoints.

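### Loosening is counted from films only and filtered by visit-window rules, so a humeral component removed for aseptic loosening can go uncounted in the loosening endpoint

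*SAP*

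**What the plan says.** **Event definition.** SAP 1.3 reads: "Based on radiographic data, time to aseptic loosening will be characterized by survival analysis using Kaplan-Meier methodology", with aseptic loosening itself as the event. Protocol 7.9.3 reads: "The number and percentage of radiographic evidence of loosening will be presented at each planned time point through 120 months, including estimates of survival". SAP 9.7 adds the Kaplan-Meier mechanics (Greenwood variance, complementary log-log intervals, at least 40 at risk) but no event definition.

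**Films.** After the immediate post-operative film, Protocol 5.3.2 schedules them at "3, 12, 24, 60 and 120 months post treatment – Grashey AP and Axillary view required". Table 1 also marks radiographs for unscheduled visits, and Protocol 5.5 sends all radiographs to the imaging vendor.

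**Window rules.** Protocol 7.9.2 and 7.9.3 apply the section 7.4 windows to the loosening endpoint. Section 7.4 maps unscheduled data to a window by date and then says: "If multiple records are allocated to the same analysis visit and one of the records is the planned collection, that record will be maintained". SAP section 4 has a different rule: where several visits fall in one interval, the latest with complete data is used.

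**Removal.** Removal of a humeral component for any reason is the event in overall survivorship (Protocol 7.9.2, SAP 9.6) and a failure criterion in the primary composite. SAP 1.4 gives periprosthetic fracture its own cause-specific component survival; loosening has no counterpart. SAP 9.8.2 censors survival endpoints for withdrawal only. Protocol 5.6 does not list revision as a ground for withdrawal; its investigator-led ground is general: "Subjects may be withdrawn by the investigator if they consider that the subject is unable to fulfil their requirements of participation".

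**Population.** Secondary and tertiary endpoints use the whole Safety Population, with no stated cut-off at revision.

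**The concern.** A component that loosens and is taken out is the clearest form of loosening failure. Under a film-only definition it enters the loosening analysis only if someone took a film before the removal and the vendor read it as loose. The longest intervals between scheduled films are from 24 to 60 and from 60 to 120 months, so that is where a removal without a preceding study film is most likely.

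The window rules add a second route for losing cases. An unscheduled film that does show loosening can be displaced by another record in its window, or have no window at all. Both routes omit true loosening cases, so the film-only definition tends to make the device look better on this endpoint.

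A related silence concerns the Constant-Murley, Oxford and EQ-5D-5L summaries. With no rule on revision, scores obtained after a removal enter the means by default, because the subject stays in the Safety Population. The means then mix results with and without the study component in place, while the stated secondary objective is clinical and radiographic performance.

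**Working it through.** **1. Which removals are captured.** Reading the passages together:

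| Situation | Loosening Kaplan-Meier (SAP 1.3) | Per-visit percentage (Protocol 7.9.3) | Overall survivorship |
|---|---|---|---|
| Removed for loosening, no earlier film read as loose | Not an event | Not counted | Event |
| Removed for loosening, earlier unscheduled film read as loose | Can be an event; whether all films or only windowed records are used is not stated | Depends on the window rules | Event |

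**2. Film spacing**, from the target days and windows in Protocol Table 2 and SAP Table 1:

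- 24 to 60 months: targets 1825 − 730 = 1095 days (3.0 years); longest allowed 2005 − 646 = 1359 days (3.7 years).
- 60 to 120 months: targets 3650 − 1825 = 1825 days (5.0 years); shortest 3470 − 2005 = 1465 days (4.0 years); longest 3830 − 1645 = 2185 days (6.0 years).
- Days belonging to no window between the 60- and 120-month visits: 2006 to 3469, that is 3470 − 2005 − 1 = 1464 days. An unscheduled film then has no analysis visit for the percentages.

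**3. Record selection inside one window.** Take the 24-month window (days 646-1644) with a planned film at day 730 showing no loosening and an unscheduled film at day 1200 read as loose.

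- Protocol 7.4 keeps day 730: not counted as loose.
- SAP section 4 keeps day 1200 if complete: counted as loose. But a complete film after a removal later in the same window would displace it.

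The two documents give different answers for the same subject, and each can lose a film that shows loosening.

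**4. Size.** The plan has no loosening or removal rate to reproduce. The denominator of 133 is borrowed from the sample-size section (157 × 0.85 = 133.45). An exact binomial check at N = 133 (75% against 85%, one-sided 0.025) needs 110 successes and gives alpha 0.0223 and power 0.808, so the planned figure stands. It does not bear on loosening.

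With n at risk, m cases seen on film, k loosening removals not seen on film, and no other censoring:

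- film-only survival ≈ 1 − m/n
- survival counting removals = 1 − (m + k)/n

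| n | m | k | Film-only | Removals counted |
|---|---|---|---|---|
| 133 | 0 | 1 | 100% | 1 − 1/133 = 99.2% |
| 133 | 0 | 3 | 100% | 1 − 3/133 = 97.7% |
| 133 | 0 | 5 | 100% | 1 − 5/133 = 96.2% |
| 133 | 0 | 8 | 100% | 1 − 8/133 = 94.0% |
| 133 | 2 | 5 | 98.5% | 1 − 7/133 = 94.7% |
| 100 | 0 | 1 to 8 | 100% | 99.0% to 92.0% |

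The values of m and k, and n = 100, are assumptions. The 133 is a 24-month figure; fewer subjects are likely to be at risk at 60 and 120 months, and each uncounted removal then weighs more.

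**The case against.** The best defence has four parts.

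- **Unscheduled films are provided for.** They are marked in Table 1 and go to the vendor, and SAP 1.3 does not restrict itself to planned films. This stands: a reader might infer that a component removed for loosening between planned films can never be an event, and the documents do not support that. A pre-removal film read as loose can be a Kaplan-Meier event. The gap is firm only where no such film exists, and for the percentages where the window rules drop it.
- **Removals are reported elsewhere.** This also stands: they are events in overall survivorship at 24, 60 and 120 months. But that analysis pools all reasons and gives no loosening rate.
- **Radiographic loosening is a legitimate endpoint in its own right.** Fair, and a reason to keep the film-only percentages. It does not justify a time-to-loosening curve that omits removal for loosening when fracture gets a cause-specific analysis.
- **Silence is not a rule.** A reader might infer that films taken after removal are counted as GLOBAL ICON results. The documents do not say so: the endpoint concerns loosening of that component, and the vendor's reading protocol (Exhibit B) is not available here. For scores the inference is stronger, since the Safety Population has no cut-off at revision, but it is still a default and not a stated rule. Summarising everyone regardless of revision is a defensible choice if labelled as such. Nor does every removal mean a wholly different implant, since only the head or only the anchor plate may be removed.

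These endpoints are also exploratory, with no labelling claims (SAP section 6 and 9.7). That limits the consequence but leaves the definition as it is.

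**Conclusion.** The point holds in a conditional form. As written, a humeral component removed for aseptic loosening is not a loosening event unless a film before removal is read as loose, and such a film can still be lost from the per-visit percentages through Protocol 7.4, SAP section 4 or the unassigned days 2006-3469. Loosening can therefore be understated.

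The size cannot be determined from the documents. Under the stated assumptions (133 at risk, none loose on film, 1 to 8 uncounted removals, no other censoring) loosening-free survival is overstated by 0.8 to 6.0 percentage points. If every removal for loosening has a prior film read as loose and the Kaplan-Meier analysis uses all films, that curve loses no cases and only the percentages are exposed.

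A reader might also infer that the primary result is at risk. It is not: removal is itself a failure criterion in the composite. The effect is confined to secondary and tertiary endpoints, but it calls for a change of definition and not merely added detail.

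**What to change.** - **Event.** In SAP 1.3 and 9.7 and Protocol 7.9.3, define time to loosening as the first of (a) aseptic loosening on any film, planned or unscheduled, inside or outside a window, or (b) removal of a humeral component with aseptic loosening recorded as the reason, dated at removal.
- **Other removals.** Censor at removal for any other reason. This treats those removals as uninformative about loosening; the SAP should state that assumption, since they are strictly competing events.
- **Reporting.** Give cumulative loosening on this definition beside the film-only per-visit percentages, labelled so that the two are not confused.
- **Record selection.** Reconcile Protocol 7.4 with SAP section 4 so that one rule governs the per-visit summaries.
- **Scores.** For Constant-Murley, Oxford and EQ-5D-5L, add a summary restricted to assessments made with the study component in place, beside the all-subjects summary.

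The cost is SAP and Protocol wording and minor programming. The films already go to the vendor, and the reason for removal is already needed for the fracture survivorship endpoint. The downside is a slightly higher reported loosening rate and one extra set of summaries.
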